Caloric restriction (CR) (reducing caloric intake up to 50% of normal calorie intake per day)⁸ is a common dietary interventional approach for weight management and cardiometabolic health improvement in adolescents and adults with obesity.⁹ However, studies have shown that CR is hard to maintain, and individuals tend to re-gain the weight after the intervention is completed.¹⁰ Time restricted eating (TRE) has been suggested as an alternative to CR.¹¹ TRE, a type of short-term fasting, is defined as periods of no energy (calories) intake followed by periods of ad libitum (as much as desired) energy intake.¹² The fact that TRE does not intentionally limit energy intake, while CR does, could make it more appealing to individuals with respect to adherence, acceptability and efficacy.¹³ TRE has been shown to be an effective strategy in reducing body fat percentage and waist circumference in adolescents and adults with obesity.^{13,14}

Moreover, high-intensity interval training (HIIT), repetitions of a short period of intense activity followed by a low intensity break, has shown to be effective in improving cardiometabolic health (including lipids, blood pressure, and insulin sensitivity) in adults with obesity compared with other traditional exercise.¹⁵ In addition to its benefits on cardiometabolic health, previous studies have suggested that HIIT can be a time-efficient strategy to enhance body composition and cardiopulmonary fitness in adults with obesity.¹⁶

However, it is unknown if TRE or HIIT will produce a greater improvement of cardiometabolic health. Therefore, the goal of this proposed study is to examine the independent and combined effects of a 4-week TRE and HIIT intervention on cardiometabolic biomarkers in adolescents and young adults.

4. Methods

4.1. Provide a detailed description of what participants will be required to do; including any technical terms or procedures.

Participants: A total of 50 adolescents (age 14-17 years old with sex- and race-specific BMI percentile $\geq 85^{\text{th}}$) and young adults with overweight and obesity (age 18 to 30 years old with BMI $\geq 25 \text{ kg/m}^2$) will be recruited for the study. This is a randomized control trial with 50 participants randomly being assigned into 3 groups: TRE intervention (n=20) or HIIT intervention (n=20), and control (n=10). The following below outlines what participants will be asked to do during each lab visit and during the 4-week of intervention.

A) Pre-lab Contacts:

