
Participants will be recruited via flyers and social media posting. Those who are interested in participating in the study will tell the researchers if they are interested in participating in the research study or will reach out via email. We will explain the purpose of the study, as well as study procedures to the potential participant. We will also provide copies of the written consent document and confirm that participants meet the inclusion criteria during this initial exchange. During this initial exchange, we will verify that the potential participant has met each of the inclusion criterion, listed on the flyer. If the participants need further clarity, or have more questions, we will provide them with a phone number for them to call us so we can answer their questions with more detail. If the potential participant expresses continued interest in enrolling in the study, we will schedule a time for them to come to the Clinical Research Laboratory (CRL) on the Syracuse University campus (Women's Building Room 303) so that we may guide them through the written consent document and begin the consent process.

If participants are interested and eligible, they will be instructed via email (1-2 days prior to actual visit days) to wear comfortable, normal, everyday athletic wear for their in-person visits. Participants will be asked to come to the SUNY Upstate Clinical Research Unit followed by SU Clinical Research Laboratory Visit after an overnight fast of 10-12 hours.

B) Pre-Intervention Lab Visits:

All data are collected following standardized procedures and by the same investigators at all timepoints to minimize potential errors of measurements. All participants will provide written informed consent prior to study involvement in accordance with university institutional review board guidelines. The following outlines the specific measurements that will be taken and the specific protocol for lab visit one.

(a) SUNY Upstate Visit (Clinical Research Unit):

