- Participants' lipid profile will be collected by Cholestech Analyzer using a blood sample obtained via a finger stick (Figure 2). Participants will select which finger they wish to use, then the researcher (wearing gloves) will clean the fingertip with an alcohol swap. Then, the researcher will "stick" the finger to draw blood. The first drop of blood will be wiped away, and the second drop will be collected and used for analysis. This may cause slight discomfort but is relatively quick and painless. After this the researcher will provide a clean gauze, to clean the area, and a band-aid (if needed).

- We will gain parameters related to cardiovascular function by using a blood pressure monitor. Participants will be asked to sit quietly for five minutes with minimal movement. After this we will place the cuff on their right upper arm (bicep area) and start the measurement. The cuff will inflate, deflate, and then reinflate again. We will ask participants not to move during this process. All of the equipment will be disinfected prior to distribution with disposable wipes (antiviral/antibacterial/antifungal) by a researcher wearing gloves before and after every time collection is performed on a participant.

- We escort participants across the hall (less than 10 feet) to the Human Performance Lab where we will take the following pre-clinical marker (Carotid-femoral pulse wave velocity [PWV]) of CVD. Participants will be escorted to a padded exam table. They will lie down and rest for approximately 5 minutes. Blood pressure in the upper arm will be measured using an automated device with a cuff that wraps around the upper arm and inflates and deflates, applying pressure to the arm. Next, we will obtain blood pressure in the wrist (radial artery), neck (carotid artery), and upper leg (femoral artery) using an applanation tonometer (SphygmoCor, AtCor Medical). This technique is non-invasive, requiring approximately 5 minutes for completion. A picture of the technique is attached. A tonometer is a very sensitive force transducer (similar in appearance to a watch battery affixed to a pen). This pen is placed over the artery of interest providing an accurate recording of the blood pressure wave. With each pulsation of the arterial pulse, a force is generated against the tonometer. The tonometer records this force wave

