(b) High Intensity Interval Training (HIIT) trial: The 4-week HIIT intervention will use a stationary bicycle performed 3 times/week (a total of 12 sessions over the 4-week), performing at the CRL. All participants will perform a 20-minute HIIT protocol (20 repetitions of 10-seconds work time followed by 50-seconds resting/active recovery for the first two weeks, and 10 repetitions of 20-seconds work time followed by 100-seconds resting/active recovery for the rest of two weeks; targeted 90% HR_{max}) after 5-minute warm-up (10% HR_{max}). The supervisor (PI: [name] and/or Graduate researcher: [name]) will provide encouragement and supervision for exercise adherence. Heart rate (Polar, Polar Electro Oy, Kempele, Finland) and rating of perceived exertion (RPE; detail described in the questionnaire section) will be recorded.

(c) Control group: Participants randomized into the control group will be told to maintain their daily lifestyle and dietary habits for the duration of the four weeks.

D) Post-Intervention Lab Visits:

Following completion of the 4-week intervention, individuals will be asked to come back to undergo same screening/measurements of the Pre-Intervention Lab Visit (SUNY Upstate and Syracuse University visits). An email will be sent to participants on their last day of the intervention with available time and dates for their visit. This will ensure all individuals will be tested with a similar fasting schedule, regardless of what group they were in.

4.2. Describe how you will have sufficient time to conduct and complete the research?

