The Human Performance Lab (Women's Building #306) is a 900 sq foot research space dedicated to the non-invasive measurement of vascular structure and function (former direction: [name]; currently being managed by [name]). The pre-clinical Markers of CVD measurements will be performed at HPL. The proposed study is being conducted in the Human Performance Lab (HPL). The HPL is a 900 sq foot research space dedicated to the non-invasive measurement of vascular structure and function. The space consists of a separate conference room area for a private consent process, dedicated cardiovascular testing space, and separate cubicles for graduate students. For the purposes of this specific study, the HPL is equipped with 1 Bod Pod, 1 Bioelectrical Impedance Scale, 1 laser stadiometer, 3 digital scales, 8 blood pressure monitors with central hemodynamic capabilities, 2 heart rate monitors (First Beat), a Watt bike for testing exercise capacity, a clinical-caliber high-end ultrasound, and Sphygmocor tonometer machine for the assessment of arterial stiffness and an Angioscan device to measure finger blood vessel reactivity. Moreover, Clinical Research Unit at SUNY Upstate, directed by [name] (scientific consultant of [name]), have been dedicated to the metabolic testing including oral glucose tolerance test with the purpose of research projects related to individuals with type 2 diabetes. The approval letter from SUNY-Upstate Medical University's IRB Office will be submitted once the protocol is approved. Furthermore, the data analysis will be conducted on Syracuse University campus, including [name] ([name]), CRL and HPL in Women's Building using computers and programs provided by the department.

5.2. List all Performance Sites Other than SU (insert additional rows if needed).

(This may apply when a SU investigator collaborates with a non-SU investigator or institution or an agency/organization will provide space to perform the research. Please check all that apply and add additional sites. Each will require a letter of cooperation and/or IRB approval.)

Check all that apply	Name of Performance Site (list all participating sites below)	IRB Approval and/or Letter of Cooperation
	SUNY Upstate Medical University	 Attached  Pending
	*Syracuse City Schools	 Attached  Pending

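### Seated blood pressure comes from one started measurement with one or at most two readings and no stated value for analysis; averaging three readings would gain precision at little cost

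*Protocol*

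**What the plan says.** The seated procedure is in Protocol section 4.1 B)(b), Syracuse University Visit. It opens with a rest period: "Participants will be asked to sit quietly for five minutes with minimal movement". Then: "After this we will place the cuff on their right upper arm (bicep area) and start the measurement". The next sentence describes what the participant will experience: "The cuff will inflate, deflate, and then reinflate again". The rest of that bullet asks participants to keep still and covers disinfection of the equipment.

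The section gives no number of recorded readings, no interval between them, no purpose for the second inflation, and no rule for the value carried forward.

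Four other places bear on this:

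- Section 4.1 B) opens with a general assurance: "All data are collected following standardized procedures and by the same investigators at all timepoints to minimize potential errors of measurements".
- Section 4.1 B)(b), in the pulse wave velocity bullet, has a separate upper-arm pressure taken with the participant lying down.
- Section 4.1 D) repeats the pre-intervention measurements after the 4 weeks.
- Section 5.1 lists, among the Human Performance Lab equipment, "8 blood pressure monitors with central hemodynamic capabilities", without saying which device takes the seated reading.

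**The concern.** Blood pressure is one of the measures taken before and after the intervention, and section 3.1 counts it within cardiometabolic health. A pre-to-post change carries the reading error of both visits. With arms of 20, 20 and 10, and the comparison with control limited by its 10 participants, avoidable reading error widens the interval for any effect on blood pressure.

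What the text describes allows one reading per visit, or two if the second inflation is a repeat. A later analysis plan can choose among recorded values, but it cannot recover readings that were never taken. The number of readings therefore has to be settled before data collection. The cuff is already in place and the participant already rested, so further readings are nearly free.

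**Working it through.** **Inputs from the protocol.** TRE 20, HIIT 20, control 10 (section 4.1, Participants); 20 + 20 + 10 = 50, which agrees with the stated total. One seated sequence per visit, with the same measurements at both visits. The protocol gives no blood pressure SD and no power calculation, so there is no figure of its own to reproduce.

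**Assumptions, not in the documents.** Within-visit SD of a single reading s_w = 4–8 mmHg, central value 6. Within-person visit-to-visit SD s_b = 5–8 mmHg, with 8 used in the central case. Errors are independent between readings and between visits, the analysis is of unadjusted change, and all participants are retained.

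**SD of the change with k readings averaged per visit:** SD = √[2(s_b² + s_w²/k)].

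Central case (s_w = 6, s_b = 8):

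- k = 1: √[2(64 + 36)] = √200 = 14.1 mmHg
- k = 2: √[2(64 + 18)] = √164 = 12.8 mmHg
- k = 3: √[2(64 + 12)] = √152 = 12.3 mmHg

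From one reading to three, the SD falls by 1 − √(152/200) = 13%. From two averaged readings to three, it falls by 1 − √(152/164) = about 4%.

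**95% half-width, 20 versus 10:** t(28) × SD × √(1/20 + 1/10), with t(28) = 2.048 and √0.15 = 0.387.

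- k = 1: 2.048 × 14.14 × 0.387 = 11.2 mmHg
- k = 2: 2.048 × 12.81 × 0.387 = 10.2 mmHg
- k = 3: 2.048 × 12.33 × 0.387 = 9.8 mmHg

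In terms of sample size for this outcome, one reading to three is worth 200/152 = 1.3 times as many participants; two to three is worth 164/152 = 1.08 times.

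**Range for one reading to three:**

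- Smallest gain (s_w = 4, s_b = 8): 1 − √[(64 + 16/3)/(64 + 16)] = 1 − √(69.3/80) = 7%
- Largest gain (s_w = 8, s_b = 5): 1 − √[(25 + 64/3)/(25 + 64)] = 1 − √(46.3/89) = 28%

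**Range for two averaged readings to three, same corners:** 1 − √(69.3/72) = 2% and 1 − √(46.3/57) = 10%.

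**The case against.** The strongest reply is that the protocol never says a single reading is used. Two inflations follow one start; the second may be a repeat reading, and the two may be averaged. That stands. A reader might infer that the change rests on one value at each end whatever the second inflation is for, but the documents do not support this: being silent on averaging is not a decision against it. Nor does the equipment list settle the matter in the other direction. A monitor with central hemodynamic functions could use the second inflation for a waveform, but the protocol does not tie that device to the seated reading.

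A second reply is that reading counts and averaging rules usually sit in a measurement manual or analysis plan, and that the protocol promises standardised procedures. This stands in part. The choice of value can be left to such a document. But section 4.1 B) presents itself as the specific visit procedure, and for the finger stick it does say which drop is analysed. As described, the seated sequence can produce no more than two readings.

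Third, the supine reading does not serve as a repeat: the posture differs, and it belongs to the pulse wave velocity procedure.

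Fourth, even three readings leave a half-width near 10 mmHg in the central case, because visit-to-visit variation and the 10 controls dominate. That is correct, and it limits what the change can achieve.

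**Conclusion.** The point holds as a cheap improvement of minor severity. The protocol describes one started measurement per visit, giving one or at most two seated readings, and does not say what the second inflation is for or which value is analysed. The change may therefore rest on a single reading at each end; that it does so is not established.

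In the central case the gain in the SD of the change is 13% if one reading is now used and about 4% if two are already averaged. Over the assumed ranges, the one-reading gain is 7–28%. Every one of these figures depends on assumed SDs, independent errors and an unadjusted change score.

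Reading error of this kind is random and the procedure is the same in all arms, so what is at stake is precision. A reader might infer a biased comparison between arms, but nothing in the documents points to one. Blood pressure is also not named as a primary outcome.

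**What to change.** In the seated blood pressure bullet of section 4.1 B)(b), state that after the 5-minute rest three seated readings are taken on the right arm, one minute apart, with the same cuff at both visits. State that the mean of all three is analysed, and that this applies identically before and after the intervention in all three arms. Say also what the existing second inflation is for.

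The figures for three readings apply only to the mean of all three. Discarding the first and averaging the last two corresponds to k = 2 in the model: a gain of 1 − √(164/200) = about 9% over one reading, and none over two readings already averaged.

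The cost is about 2–3 minutes and one or two more cuff inflations per visit, in a visit that section 4.2 puts at 5–6 hours. The device and staff stay the same. The change must be made before data collection starts.

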and reconstructs it into a pressure wave. From this wave, we can estimate blood pressure in this artery and calculate the stiffness (or how elastic the artery is). This measure takes 5-minutes to complete.

C) Randomization:

Upon completion of the Pre-Intervention Lab Visit, participants will be randomly assigned into one of three groups: (a) TRE, (b) HIIT, and (c) Control. The randomization will be done separately for adolescents and young adults [with the exploratory purpose of future analysis on age-specific difference in interventional effects on cardiometabolic health]. Within each group, we anticipate that there will be an equal number of adolescents and young adults.

(a) Time Restricted Eating (TRE) trial:

Participants randomized into the TRE group will be instructed to consume all their calories within a 10-hour period. We will instruct participants that they can choose their time-window (early TRE [7am – 5pm] or late TRE [1pm – 11pm]), but it must remain constant for the duration of the study. Further, we will give no restrictions on the type of foods and/or the quantities individuals can consume. We will ask individuals to maintain their diet for the duration of the study. Participants will be given clear instructions on their diet and how to use the “MyFitnessPal” application. Participants will have their total daily energy requirement calculated using the following formula (Basal metabolic rate [BMR] x activity level) and will be told to eat that amount within their allotted time window. BMR will be calculated when participants have their body composition taken by the InBody. Participants will be told to start their 4-week diet the following day after visit.

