12.3. Does this research involve more than minimal risks to participants?

No. (Skip to Section 13)

Yes. If yes, please provide plan for monitoring the data collected to ensure the safety of participants. (Your data safety monitoring plan must include the following: Description of who will monitor the data, what data will be monitored, how frequently will it be monitored, what analysis will be performed on the data, what decision rules (e.g. stopping rules) will be considered, if unexpected harms will be detected promptly, if an increased frequency or severity of unexpected harms will be detected promptly, if the protocol will be stopped once harms are proven to outweigh benefits.).

13. Benefits

13.1. Describe any benefits to the participants in general. Incentives, such as course credit, payment, gift cards, entry into a raffle, etc. are considered an inducement to participate in the research and should NOT be described as a benefit.

By participating in this research, all participants will examine how they are healthy and be given their health information such as metabolic function, body composition, blood pressure, lipid profile, cardiovascular function with no cost.

Time restricted eating has been shown to be an effective strategy in reducing BMI, and body fat percentage in overweight and obese adults. By partaking in this study, participants could potentially reduce their weight, which has been shown to improve cardiometabolic health.

13.2. Society at large.

TRE and HIIT may prove to provide beneficial effects on cardiovascular health. Heart disease is the leading cause of death in the world and places a major economic burden on the health care system.¹⁷

13.3. Explain how the benefits outweigh the risks involved.

There are minimal risks to this study. For instance, TRE and HIIT are not currently contraindicated for individuals with overweight and obesity. During the two visits to the CRL, only minimally invasive techniques (i.e. blood draws) are used and poses little risk for all involved. Therefore, with minimal risk and the potential of cardiometabolic improvements through weight loss, we feel the benefits outweigh the risks.

A number will be assigned to your protocol. Please refer to it whenever calling or writing for information.

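### The TRE arm gets three instructions on how much to eat that do not fit together, and one of them sets a daily amount, contrary to the protocol's own ad libitum definition of TRE

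*Protocol*

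**What the plan says.** All the TRE instructions stand in one paragraph, Protocol section 4.1 C(a). Participants eat within a 10-hour window of their choice, held constant for the study. On quantity, the paragraph says three things, in this order:

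1. "we will give no restrictions on the type of foods and/or the quantities individuals can consume".
2. Participants are asked to keep to their diet throughout the study.
3. "Participants will have their total daily energy requirement calculated using the following formula", namely basal metabolic rate times activity level, and participants "will be told to eat that amount within their allotted time window".

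The paragraph also introduces food logging with MyFitnessPal, and section 8.4.2 ties the TRE payments to home-based food tracking.

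Section 3.1 defines TRE as periods without energy intake "followed by periods of ad libitum (as much as desired) energy intake". It sets TRE apart from caloric restriction (CR) on this ground: "The fact that TRE does not intentionally limit energy intake, while CR does". It suggests that this could help adherence, acceptability and efficacy.

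In the other arms, section 4.1 C(b) gives HIIT participants no dietary instruction. Under section 4.1 C(c), controls "will be told to maintain their daily lifestyle and dietary habits for the duration of the four weeks".

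**The concern.** What participants are told to eat is the core of this experimental arm, and the paragraph does not settle it. The first statement leaves quantity free and the third sets it. The second could mean holding intake at its usual level.

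The two possible interventions answer different questions. Under ad libitum TRE, a spontaneous change in intake caused by the shorter window is part of the effect. Under TRE with a set daily amount, intake is steered by a formula, and the contrast with control combines meal timing with an energy prescription. Neither a positive nor a null result would mean the same thing under the two versions.

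Randomisation is not at risk, because the comparison still estimates the effect of whatever package is delivered. What is at stake is consistent delivery and what the result can be said to show.

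**Working it through.** There is no figure in the plan to reproduce, so the check is textual, with a small piece of logic and a count of scope.

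**Can one participant follow all three statements?** Let H be habitual daily intake, R the calculated requirement and I the intake during the study.

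| Statement in section 4.1 C(a) | What it asks of I |
|---|---|
| No restrictions on quantity | I is free |
| Keep to their diet (read as usual intake) | I = H |
| Eat the calculated requirement | I = R |

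- The second and third agree only if H = R. Nothing in the protocol selects participants on that basis, and H is not given.
- If H > R, the third statement is an instruction to eat less than usual. If H < R, it is an instruction to eat more.
- In either case an instruction that I = R is not the absence of an instruction on quantity, so the first and third do not fit together whatever H is.

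The second statement does not resolve this. The same paragraph also uses the word diet for the 4-week TRE regimen itself, so keeping to the diet may mean usual intake or simply staying with the regimen.

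**Does either version match the rationale?** Section 3.1 makes ad libitum intake part of the definition of TRE. A freely chosen quantity fits that definition; a set daily amount does not.

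**Is the prescription shared across arms?**

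| Arm | n | Energy or diet instruction |
|---|---|---|
| TRE | 20 | 10-hour window, plus the three statements above |
| HIIT | 20 | None |
| Control | 10 | Keep usual lifestyle and dietary habits |

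The energy target applies to TRE only.

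**Scope.** The TRE share is 20 / (20 + 20 + 10) = 20/50 = 40%. Three arms give three pairwise comparisons, and TRE enters two: TRE versus HIIT (20 v 20) and TRE versus control (20 v 10). These counts show how much of the trial the ambiguity touches. They do not measure bias.

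**Can the data repair it afterwards?** Only in part. The food log shows what participants report eating. It does not show which instruction they took as binding, or what they would have eaten without a target.

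**The case against.** The strongest defence reads the whole paragraph together: no imposed cap and no food rules, usual diet continued, and the calculated requirement offered as the amount to fit into the window. On that reading the arm changes when people eat and not how much. The requirement is a maintenance estimate and not a restriction, and it may have been meant as a guide against under-eating.

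Part of this stands. The requirement is not caloric restriction, and nothing here shows that the authors intended to limit intake. But no visible sentence calls the figure a guide, a minimum or optional, and participants being told to eat it is worded as an instruction. Nor is the coherent reading ad libitum TRE as section 3.1 defines it, so the mismatch with the rationale remains.

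It is also fair that a small team meeting weekly may deliver the paragraph uniformly. That would give consistent delivery but would not tell a reader which intervention was tested. An instruction given only in the dietary arm is a legitimate part of a package, provided the package is described as such.

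A reader might go further and infer that the requirement contradicts the benefit statements in sections 13.1 and 13.3, since eating at requirement plans no energy deficit. The documents do not support that. Section 13.1 is hedged ("participants could potentially reduce their weight, which has been shown to improve cardiometabolic health"), section 13.3 speaks only of "the potential of cardiometabolic improvements through weight loss" and covers TRE and HIIT together, and a person who habitually eats above the requirement would be told to eat less. A planned deficit of zero is true only by definition and says nothing about actual intake.

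**Conclusion.** The point holds as an internal inconsistency in the definition of the TRE intervention. Section 4.1 C(a) leaves quantity free, asks participants to keep to their diet and prescribes a calculated amount, without saying which governs. The prescription departs from section 3.1 and applies to one arm only. As written, a TRE effect could not be attributed clearly to ad libitum time restriction or to time restriction with an energy prescription.

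The inconsistency affects the definition of one arm of 20 and two of the three pairwise contrasts. The size and direction of any effect on outcomes cannot be derived, because the protocol gives no habitual intakes and no expected adherence to the target. The randomised comparison itself remains valid.

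This rests on one assumption: that the participant-facing consent and assent wording, which is not visible here, does not already settle the matter. It should be corrected, but it is a matter of wording and not a flaw in the design as a whole.

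**What to change.** Preferred change, which keeps the arm as section 3.1 defines it:

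- In section 4.1 C(a), delete the clause saying that participants "will be told to eat that amount within their allotted time window". State that the calculated requirement and the MyFitnessPal log are used for monitoring only.
- Reword the sentence on keeping to their diet so that it does not fix quantity. For example: participants keep their usual choice of foods, and how much they eat inside the window is left to appetite.
- Check that the two consent forms and the one assent form (sections 9.1 and 9.2) say the same.

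If a requirement-matched arm is what is intended, remove the reference to quantities from the no-restrictions sentence, make the keep-to-diet sentence consistent with the target, revise the ad libitum rationale in section 3.1, and limit conclusions to TRE at a prescribed energy intake.

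The cost of the preferred change is two edits in one paragraph, an IRB amendment and a check of three forms. It adds no procedure, because food tracking is already planned and paid for. The alternative also needs the edits to section 3.1.
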